Even though EPIC's Risk of Unplanned Readmission model was developed for the acute care hospital setting, variations in demographic features, disease prevalence and differences in test conditions (e.g. defining criteria of relevant readmissions, time frame of measurement) entail external validation prior to routine application in the Swiss acute care hospital setting.

For this reason, the main objective of this study is to externally validate EPIC's Risk of Unplanned Readmission model as i) a predictor of all-cause unplanned hospital readmissions within 30 days, ii) a predictor of unplanned readmissions within 18 days according to SwissDRG's specification, and to compare the model with the LACE+ index and the SQLape® readmission algorithm.

METHODS

Study design & study sites

This monocentric, retrospective, diagnostic cohort study will include all inpatients from the Lucerne Cantonal Hospital, which is the largest provider of basic and highly specialized healthcare services in Central Switzerland. This study is designed not to meet the criteria for research involving human subjects. The Ethics Committee Northwest- and Central Switzerland (EKNZ) will be informed and asked for an ethics waiver.

Participants

All inpatients, aged one year or older (max. 100 years), who were hospitalized either between the 1st of January 2018 and the 31st of December 2018, or between the 23rd of September and the 31st of December 2019 will be included. Cases will be inpatients that experienced (i) an unplanned readmission within 18 days according to SwissDRG's specifications; (ii) an unplanned all-cause readmission within 30 days after the index discharge. The control group will consist of individuals who had no unplanned readmission within the relevant days after the index discharge.

Exclusion criteria will be (a) admission/transfer from another psychiatric, rehabilitative or acute care ward from the same institution, (b) discharge destination other than the patient's home or (c) transfer to another acute care hospital, both being considered as treatment continuation; (d) foreign residence, (e) deceased before discharge, (f) discharged on admission day, (g) refusal of general consent, and (h) unknown patient residence or discharge destination.

For individuals with multiple readmissions during the study period, only the first readmission will be included into the analysis.

Predictors

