Backward feature selection was performed (with a significance level of $\alpha = 0.05$) and resulted in 11 significant covariates. The final point score ranges from -15 to 114, a score greater than 90 is considered with a high risk for unplanned readmission or death within 30 days after discharge. The internal validation of the 11-item index, excluding the Canada specific case-mix group (CMG) score,

showed reasonable discrimination with an AUC of the ROC curve of 0.743 for all-cause unplanned readmission, but poor calibration (H – L statistic 58.93, p < 0.0001).

SQLape®: The SQLape® readmission risk model (Striving for Quality Level and analyzing of patient expenditures), a computerized validated algorithm, was developed in 2002, in Switzerland (6). The SQLape® prediction model predicts unforeseen hospital readmission within 30 days after hospital discharge. The development sample consisted of 131'809 inpatient stays from 49 Swiss acute care hospitals, of which 12 hospitals were located in the French speaking part of Switzerland.

Healthy newborns, residents outside of Switzerland and elective surgical patients that could usually be performed as day surgery were excluded. After backward elimination was performed, the Poisson regression model consisted of six variables/SQLape variable groups. Of the beforementioned 131'809 inpatient stays, 66'069 were used for internal validation. The discrimination was measured by the Harrell's C statistic, which is also referred to as the estimated area under the Receiver Operating Characteristics (ROC) curve (AUC). A value of 0.72 showed reasonable discriminative ability.

Outcome(s)

The predicted outcome of all prediction models will be compared with the observed outcome. Both outcomes will be assessed retrospectively. The primary outcome will be the all-cause unplanned readmission to the same hospital within 30 days after the index hospital discharge. An unplanned readmission will be defined as an urgent readmission, i.e. not scheduled in advance and requires treatment within 12 hours.

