The secondary outcome, as defined by the SwissDRG, will be the unplanned readmission to the same hospital, that resulted in a case merging (19). According to SwissDRG, patient records of the index admission and the nth readmission are merged into a single case if they fall into the same major diagnostic category (MDC), occurred within 18 days after the index/preceding hospital discharge date, and are not excluded from the case merging rule.

Sample size

Sample size calculations resulted in a aspired sample size of at least 1000 participants (500 cases and 500 controls) for each site. The proposed sample size is based upon precision. 500 cases and 500 controls will ensure that the half-width of a 95% confidence interval for sensitivity and specificity (using frequencies of predicted vs. actual outcome) does not exceed 5%; even for a point estimate of 50%, leading to the widest possible confidence interval, the half-width is supposed to remain slightly below 4.5%. This can be considered to be an appropriate target precision for the purpose of this study.

Data collection

Demographic and administrative data, medications, orders, International Classification of Disease (ICD) diagnosis codes, and biological data will be extracted in an anonymized manner from electronic patient records. Data covering the initial period will be retrieved from several different Information Systems (e.g. Dorner Lab. System, NEXUS/Medfolio etc.). Because of the introduction of a new Clinical Information System (CIS) in 2019, data covering the latter period of interest (23rd of September to 31st of December 2019) will be retrieved separately, i.e., from the new Clinical Information System from EPIC Systems corporation.

Missing data

Missing data required to compute the prediction models will be handled as following: Missing biological data (hemoglobin, sodium, calcium etc.) will be coded as normal values. Missing comorbidity and medication data will be considered as absence of the condition and no active medication, respectively. Missing order data (imaging, restraining, electrocardiogram) will be considered as an intervention not ordered. Lastly, missing records of utilization of health care resources (e.g. ED visits, scheduled future admissions etc.) will be considered as non-utilization.

Missing demographic or administrative data to describe patient's characteristics will result in the patient's exclusion from the analysis.

Statistical analysis

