EPIC's Risk Setting: U.S. multi-centric study, including more than 275'000 adult inpatients from 26 of different hospitals; the national readmission rate equals 10%-15% (20, 21) Unplanned Eligibility criteria: No relevant differences Readmission Outcome: The primary outcome was the unplanned readmission within 30 days of the index hospital discharge, defined according to the Centers for Medicare & Medicaid Services (CMS) **Planned Readmission algorithm Predictors:** ICD-10 codes vary slightly by country - diagnosis grouper will need modification; medication vendors and medicinal products can vary from country to country – ATC groups will need modification; less frequent ED use compared to the US - hence, the predictor might have a smaller effect (22, 23) LACE+ Setting: Multi-centric, Canadian study including medical and surgical adult inpatients who had been discharged to the community from an Ontario hospital; the study involved 500'000 randomly selected patients; the Canadian national readmission rate equals 9%-10% Eligibility criteria: All medical and surgical patients, excluding discharges to rehabilitation and long-term care facilities, patients who underwent same-day surgeries, psychiatric and obstetric and patients who were ineligible for health care coverage in Ontario. Outcome: The primary outcome was death or urgent readmission within 30 days of hospital discharge, the secondary outcome was only urgent readmission within 30 days of hospital discharge; variations in regard to the excluded procedures and diagnoses can be expected; the development sample covered, to some extent, external readmissions, i.e. patients being readmitted to another hospital - not considering external readmissions in the validation study can lead to over- or underestimation **Predictors:** The original study included the predictor variable case-mix group (CMG) to

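### The 2019 retrieval dates are the same as the index window: if followed as written, follow-up is incomplete for December 2019 discharges, and earlier utilisation is coded as non-use unless it was migrated

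*Combined protocol and SAP*

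**What the plan says.** - **Index window (Methods, Participants).** Inpatients from calendar year 2018 are eligible, "or between the 23rd of September and the 31st of December 2019 will be included". The criterion is being hospitalised in the window, not being discharged in it.
- **Retrieval (Methods, Data collection).** "Data covering the initial period will be retrieved from several different Information Systems", with no dates attached. For 2019, "data covering the latter period of interest (23rd of September to 31st of December 2019) will be retrieved separately", and the source named is the new clinical information system.
- **Outcomes (Methods, Outcome(s)).** "The primary outcome will be the all-cause unplanned readmission to the same hospital within 30 days after the index hospital discharge". The secondary outcome, SwissDRG case merging, uses 18 days.
- **Controls (Methods, Participants).** "The control group will consist of individuals who had no unplanned readmission within the relevant days after the index discharge". Nothing requires those days to have been fully observed.
- **Missing utilisation (Methods, Missing data).** "missing records of utilization of health care resources (e.g. ED visits, scheduled future admissions etc.) will be considered as non-utilization".
- **ED use (Development vs. validation).** ED use is treated as a predictor in both the EPIC model and LACE+. A smaller effect is already expected because of "less frequent ED use compared to the US", with a parallel remark for Canada.

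No section gives an outcome retrieval end date, a look-back start date, a rule for incomplete follow-up, or any linkage or migration between the old and new systems. Limitations covers undocumented parameters and same-hospital readmissions, but not loss at the edges of the window.

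**The concern.** A retrieval window equal to the index window is too short at both ends.

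**Late end.** Readmissions in January 2020 after December discharges would not be seen. With no rule for incomplete follow-up, these patients would by default be counted as controls. That last step is an inference, because the protocol does not say it.

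**Early end.** A patient admitted soon after 23 September 2019 has almost no searchable history in a retrieval that starts that day. The missing-data rule then turns history that was never searched into a recorded zero, indistinguishable from true non-use.

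The study exists to measure calibration and discrimination. Missed events lower the observed rate and false zeros alter the predicted risk. Both feed the calibration plot, the Brier score and Net Benefit. The dated cut applies to 2019 only, and the two periods come from different systems, so an artefact of retrieval could appear as a difference between periods. Unretrieved ED visits would also resemble the lower ED use that the protocol already expects.

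**Working it through.** The plan gives no figure for follow-up completeness. Its one related design figure is the confidence-interval half-width under Sample size, which reproduces: 1.96 × √(0.25/500) = 4.38%, against a stated value slightly below 4.5%. If all 500 cases came from the 2019 window and 15.5% were missed, 500 × 0.845 = 422.5 would remain, with half-width 4.77%. That is still under 5%, so precision is not the problem. The issue is misclassified outcomes and predictors.

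**Inputs from the protocol.** The 2019 window, 23 September to 31 December, is 100 days. Both windows together are 365 + 100 = 465 days. Follow-up W is 30 or 18 days.

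**Assumptions.** Index discharges are even over the days of both windows, and event rates are equal. Readmission timing within W days lies between exponential with a 10-day mean (front-loaded) and uniform. Only the dated 2019 cut is applied.

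**Days without full follow-up.** A 1 December discharge plus 30 days is 31 December, so discharges on 2-31 December are incomplete: 30/100 days. For 18 days, 14-31 December: 18/100 days.

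**Events missed.** Let k be the days from discharge to 31 December 2019 and F the timing distribution within W days. The missed share is Σ(k = 0 to W−1) [1 − F(k)] divided by the number of index days.

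| Outcome | Sum, exponential to uniform | Share of 2019 events (/100) | Share of pooled events (/465) |
|---|---|---|---|
| 30-day | 8.94 to 15.50 | 8.9-15.5% | 1.9-3.3% |
| 18-day | 6.94 to 9.50 | 6.9-9.5% | 1.5-2.0% |

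**Effect on the observed 30-day rate.** The hospital's own rate is not given. As an illustration, take the range spanned by the Canadian (9%-10%) and US (10%-15%) national rates in Development vs. validation.

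- Pooled: 9% × 0.0192 = 0.17 and 15% × 0.0333 = 0.50, so about 0.2-0.5 percentage points too low.
- 2019 alone: 9% × 0.0894 = 0.8 and 15% × 0.155 = 2.3 points too low.

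**Direction of miscalibration.** If m is the missed share and d the relative fall in mean predicted risk from false zeros (assumed downward), the observed/expected ratio is multiplied by (1 − m)/(1 − d). It is unchanged at d = m. For 2019 alone, a fall smaller than 8.9-15.5% looks like over-prediction and a larger one like under-prediction. The documents give no value for d.

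**Look-back coverage.** Look-back lengths L are not in the documents. As an assumption only, with even admissions over the 100 days and nothing before 23 September retrieved, the average observed fraction is the mean over j = 0 to 99 of min(L, j)/L. This gives 84.5% for L = 30 days, 54.5% for 90, 27.5% for 180 and 13.6% for 365. These are shares of the look-back that are covered, not effects on predicted risk.

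**2018.** No retrieval dates are stated for the initial period, so no loss is computed there.

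**The case against.** The strongest reply is that the quoted sentence explains which system supplies the data and is not an extraction cut-off. On that reading the dates only label the cohort. The primary outcome is defined over 30 days, controls must have had no readmission in the relevant days, and the protocol is dated 18.02.2020, 49 days after 31 December 2019. All of this suggests that full follow-up was intended. It stands, and makes the point conditional: a reader might infer that the plan loses the January readmissions, but the documents do not show that.

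Other stronger readings also fail:

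- **That 8.9-15.5% is the effect on the study's results.** It is the share for 2019 alone, and the protocol plans no analysis by period. The pooled figure is the relevant one for the analysis as written, and it is small.
- **That calibration is biased in a known direction.** Missed events and false zeros can offset each other, so the net direction is open.
- **That prior utilisation is certainly lost.** Older records may have been migrated, the look-back lengths sit in an appendix available on request, and Limitations discloses in general terms that undocumented parameters are treated as uneventful.
- **That 30 January 2020 is a sufficient end date.** This holds only if the window is by discharge date. Participants refers to hospitalisation, so stays may end after 31 December.
- **That the abstract's single continuous 2018-2019 period strengthens the case.** It conflicts with the two windows in Participants, but is a separate wording matter and adds nothing to the severity here.

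What the reply does not remove is that no section states the extension, the linkage or a rule for incomplete follow-up, while the rule turning missing utilisation into non-use is explicit.

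**Conclusion.** The point holds conditionally and should be fixed; confidence is medium. If the stated 2019 dates are applied as written, 30% of 2019 index days lack full 30-day follow-up and 18% lack full 18-day follow-up. Pooled, that is a modest loss of events and at most about half a percentage point on the observed 30-day rate; within 2019 it is large enough to distort a calibration plot. These sizes rest on even discharges, equal event rates, the assumed timing range and borrowed national rates.

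The look-back problem depends on whether records were migrated and cannot be sized from the documents. It is more than a missing detail, because the coding rule would make unsearched history look like observed non-use.

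**What to change.** 1. **Outcomes.** For each period, state that readmissions are retrieved to 30 days after the last index discharge. That is 30 January of the following year if the window is by discharge date, and later if stays may end after 31 December. Say which definition applies. Otherwise restrict index discharges to those with full follow-up.
2. **Predictors.** Retrieve utilisation over each predictor's full look-back, linking to the older systems before anonymisation. Code non-use only where the look-back was searched, and report how many patients could not be searched.
3. **Reporting.** Give calibration and discrimination by period as well as pooled, because the source systems differ.
4. **Wording, separately.** Reconcile the abstract's continuous 2018-2019 period with the two windows in Participants.

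**Cost.** A wider query, cross-system linkage and a little more analysis. With a discharge-based window, 30 January 2020 is 19 days before the protocol date, so the outcomes had already occurred. With stays ending later, follow-up was complete by 18 February only for discharges up to 19 January (19 January + 30 days = 18 February). If data really stop at 31 December and index discharges end on 1 December instead, 30/100 = 30% of the 2019 index days are lost, and 30/365 = 8.2% of the 2018 days if the same limit is needed there.

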Methods: For this reason, a monocentric, retrospective, diagnostic cohort study will be conducted. The study will include inpatients, who were hospitalized between the 1st of January 2018 and the 31st of December 2019 in the Lucerne Cantonal hospital in Switzerland. Cases will be inpatients that experienced an unplanned (all-cause) readmission within 18 or 30 days after the index discharge. The control group will consist of individuals who had no unscheduled readmission.

For external validation, discrimination of the scores under investigation will be assessed by calculating the area under the receiver operating characteristics curves (AUC). For calibration, the Hosmer-Lemeshow goodness-of-fit test will be graphically illustrated by plotting the predicted outcomes by decile against the observations. Other performance measures to be estimated will include the Brier Score, Net Reclassification Improvement (NRI) and the Net Benefit (NB). All patient data will be retrieved from electronic clinical data bases.

Discussion

This is a presentation of the study protocol only. Results and discussion will be published after completion of this study.

Others

The study protocol was approved by the Ethics Committee Northwest- and Central Switzerland (ID:2019-01861) and will be registered on ClinicalTrials.gov.

INTRODUCTION

Readmissions after an acute care hospitalization are relatively common, costly to the health care system and are associated with significant burden for patients (1-5). A readmission increases the risk of dependence and functional or psychosocial decline [5]. Moreover, a readmission increases the risk of decompensation of other comorbid conditions, thus increasing the frailty of elderly patients [6].

The belief that readmission rates are a valid indicator to assess quality of care has led to their inclusion in hospital quality surveillance (6, 7). In September 2018, the Swiss National Association for Quality Development in Hospitals and Clinics (ANQ) reported its most recent findings. Accordingly, based on 2016 figures, the number of Swiss hospitals that reported more readmissions, as expected according to their patient mix, has more than doubled. In total, 47 out of 145 hospitals reported rates (observed/expected) outside the norm, i.e. significantly higher than 1 (8). This increase (+3.3%) in observed unplanned readmissions has been ongoing since 2011 and is proving to be statistically significant (9).

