In the last few years, the observed increase in costs has been posing major challenges for the healthcare system. Healthcare costs in Switzerland have risen by a good third within the last decade (10). As one way to reduce costs and simultaneously improve quality of care, hospital readmissions receive increasing interest from policy makers. It is only relatively recently that policies were developed with the specific aim of reducing readmissions. In Switzerland, the readmission policy involves financial penalties, i.e., that patient records of the first admission and the relevant readmission are merged into a single case, if certain criteria are met. Consequently, hospitals receive only one DRG-based payment for both admissions (11). In result, and despite the fact that some readmissions cannot be avoided and the proportion of potentially avoidable readmissions (PARAs) remains debatable, health care organizations invest considerable resources into efforts to reduce hospital readmissions (12-14).

To most efficiently reduce readmissions, hospitals need to target effective discharge and postdischarge interventions at those who need them the most. One of the more recent strategies is the application of prediction models. As systematic reviews have shown, there are many models aimed at identifying those at greater risk of readmission (15, 16). The majority includes readily available predictors such as demographic and administrative data, comorbidities, laboratory, and medications (15). Among these models, the EPIC's Risk of Unplanned Readmission model, developed in 2015 for the U.S. acute care hospital setting, promises superior calibration and discriminatory abilities. The model was developed by EPIC Systems corporation based on data from 26 EPIC community member hospitals, including more than 275'000 inpatient hospital admission encounters to determine a patient's risk of unplanned readmission within 30 days of being discharged from an index admission.

RATIONALE & OBJECTIVES

Prediction models require internal and external validation. Whereas internal validations means testing the model in the population used to develop it, external validation means applying the model with its predictors and assigned weights, as estimated from the development study, to a new population; measuring the predictor and outcome values; and quantifying the model's predictive performance (calibration and discrimination).

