The following paragraph provides a description of the predictive models to be evaluated. A distinct definition of the variables included is available from the corresponding author upon reasonable request. In advance, it needs to be mentioned, that the EPIC's Risk of Unplanned Readmission and the SQLape[®] Readmission Risk model are commercially distributed products. Implicitly, due to copyright issues, not all information about the predictors required to replicate this validation study were allowed to be disclosed in sufficient detail/at all. Replicating this study requires licensing.

EPIC's Risk of Unplanned Readmission model: The EPIC's Risk of Unplanned Readmission model is a logistic regression model that predicts the risk of all-cause unplanned readmissions within 30 days of the index hospital discharge. An all-cause unplanned readmission was defined according to the Centers for Medicare & Medicaid Services (CMS) Planned Readmission algorithm (version 2.1) (17).

The data set used for the development of the model included more than 275'000 hospital inpatient encounters from 26 different hospitals. Three of these hospitals were large academic medical centers (1000+ beds each), while the others were either smaller regional hospitals or community hospitals. All included sites were chosen from very distinct geographic regions in the US to ensure a population as diverse as possible. A selection by specialties/medical disciplines was not applied; all ages; any payer; and encounters for which patients leave the hospital against medical advice were included.

After feature selection, using a least absolute shrinkage and selection operator (LASSO) penalty, the final model consisted of 27 predictive parameters.

The internal and external validation of the model showed acceptable discrimination at predicting allcause unplanned readmission within 30 days post discharge with an area under the receiver operating characteristic curve (AUC of the ROC curve) ranging from 0.69 to 0.74.

LACE+: The LACE+ risk index is a point score derived from a logistic regression model, which was developed to predict the risk of 30-day post-discharge death or urgent readmission (18). It was developed and internally validated based on a large, randomly selected, population-based sample from Ontario, Canada in 2012. The development sample excluded patients who underwent same-day surgeries, psychiatric and obstetric admissions.

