The EPIC's Risk of Unplanned Readmission model predictions and LACE+ scores will be calculated as the inverse of $1+e^{-(intercept+\beta^{1_*}x^1+\dots+\beta^{K_*}x^K)}$, where β will be the regression coefficient of each covariate (x), and K will be the total number of covariates. SQLape[®] readmission predictions will be automatically calculated by the plugin provided by the author.

To assess the performance, the traditional statistical approach is to quantify how close predictions are to the actual outcome. As overall performance measure, composing of discrimination and calibration, the Brier score will be calculated. Assessed separately, the discriminative ability will be measured using the Harrell's C-statistic, which, for binary outcomes, is identical to the area under the Receiver Operating Characteristic (ROC) curve (AUC). For calibration, the Hosmer-Lemeshow goodness-of-fit test will be graphically illustrated by plotting the predicted outcomes by decile against the observations. Furthermore, other performance measures to be estimated will include the Net Reclassification Improvement (NRI) and the Net Benefit (NB). All statistical analyses will be performed in R.

Risk groups

Risk groups will be established based on the recommendations by the developers of EPIC's Risk of Unplanned Readmission model, i.e., to use the organization's current readmission rate as baseline

risk and group as follows: "no risk = 0 – baseline", "low risk = baseline – 2 x baseline", "medium risk = 2 x baseline – 3 x baseline", "high risk = > 3 x baseline".

Development vs. validation

The differences in this validation study compared to the development studies are briefly summarized below:

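### Calibration gets a Hosmer-Lemeshow test and a decile plot, but no planned measure estimates the size of miscalibration with an interval

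*Combined protocol and SAP*

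**What the plan says.** The Rationale & Objectives section describes external validation as applying the model to a new population and "quantifying the model's predictive performance (calibration and discrimination"). The Statistical analysis section gives discrimination a single estimate, the C-statistic or AUC. Its whole provision for calibration is: "For calibration, the Hosmer-Lemeshow goodness-of-fit test will be graphically illustrated by plotting the predicted outcomes by decile against the observations". The Abstract says the same.

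The other planned measures are the Brier score, which the section itself calls an overall measure of discrimination and calibration together, the Net Reclassification Improvement and the Net Benefit. No O/E ratio, calibration intercept, calibration slope or smoothed calibration curve appears anywhere. Observed/expected ratios are mentioned only in the Introduction, as background on national hospital surveillance. The Reporting section commits to TRIPOD but names no calibration statistic.

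The Risk groups section plans "to use the organization's current readmission rate as baseline" risk, and cuts predicted risk at one, two and three times that rate.

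**The concern.** The plan's own definition asks for calibration to be quantified, yet the only dedicated output is a test and a picture. A Hosmer-Lemeshow p-value answers whether some departure was detected. That depends on how many patients there are, and it does not say whether the models are off in overall level or in spread. The protocol shows the difficulty itself: in the Predictors section it reports poor LACE+ calibration as a Hosmer-Lemeshow statistic of 58.93 with p < 0.0001, and from this nobody can tell how large the error was or in which direction.

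Miscalibration is plausible from differences the protocol lists. LACE+ was "developed to predict the risk of 30-day post-discharge death or urgent readmission". The SQLape development outcome was potentially avoidable readmission. Readmissions to other hospitals are not counted. Emergency department use is expected to carry less weight than in North America. Because patients are grouped by absolute predicted risk, miscalibration moves them between groups.

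**Working it through.** **The plan's own figure.** The Sample size section gives a worst-case 95% half-width slightly below 4.5% with 500 per group. Check: 1.96 × √(0.5 × 0.5 / 500) = 4.38%. It reproduces, but it concerns sensitivity and specificity. No precision is stated for calibration.

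**Inputs for an illustration.**
- Readmission rate 10%. Development vs. validation gives 9-10% for Canada and 10-15% for the US.
- AUC 0.743, the LACE+ value without the case-mix score.
- N = 5,000, which gives 500 events at 10%, the minimum number of cases in Sample size. N = 20,000 is an assumed larger cohort; the protocol does not state the total.
- Logit-normal risks in a full, unsampled cohort. Mean logit -2.541 and SD 0.965 reproduce the rate and the AUC.

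**Two errors.** Case A is a rate shift: 0.117 added to the logit, so O/E = 1.10 and slope 1. Case B is a slope error: slope 0.8615 and intercept -0.268, so O/E = 1.00. B was chosen to have the same Hosmer-Lemeshow power as A, so their equality is by construction.

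**Hosmer-Lemeshow power.** Ten groups, 10 df because the predictions are given from outside. With p predicted and q true decile risk, the non-centrality is (N/10) × Σ (q - p)² / [p(1 - p)].

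| N | Non-centrality (A = B) | Power | Simulated |
|---|---|---|---|
| 5,000 | 6.02 | 32% | about 37% |
| 20,000 | 24.09 | 95% | about 95% |

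The same error mostly passes at one cohort size and nearly always fails at the other, and the p-value does not distinguish A from B. With 500 events, over rates of 9-15% and AUC 0.69-0.743, power is 31-35% and the matching slope 0.82-0.86.

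**What the plot shows.** The top decile has predicted risk 30.5%, against 33.0% observed in A and 27.4% in B. In simulation at N = 5,000 that point lies above the diagonal in 88% of A cohorts and 6% of B cohorts; at 20,000, in 98.5% and 0%. So the plot usually gives direction. Its size is loose: at N = 5,000 the 95% half-width of the point is 1.96 × √(0.305 × 0.695 / 500) = 4.0 percentage points, against expected gaps of +2.4 and -3.1.

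**What the added measures would give.** With mean p(1 - p) = 0.0822 at N = 5,000:
- O/E half-width: 1.96 × √(5,000 × 0.0822) / 500 = 0.08. On the log scale, exp(±1.96 × √(0.9 / 500)) gives 0.92 to 1.09.
- Intercept half-width: 1.96 / √(5,000 × 0.0822) = 0.10.
- Slope half-width, from the logistic information: 0.11.
- In simulation the O/E interval excludes 1 in about 65% (A) against 4% (B), and the slope interval in 5% (A) against 71% (B).

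**Effect on the top risk group** (above three times the observed rate):
- A: cut-off 3 × 11% = 33%. 2.9% of patients are flagged and 3.8% truly exceed it.
- B: cut-off 3 × 10% = 30%. 4.0% are flagged and 2.6% truly exceed it.

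**Sampling.** The study is described thus: "This monocentric, retrospective, diagnostic cohort study will include all inpatients". The sample-size target is "at least 1000 participants (500 cases and 500 controls) for each site". If the latter meant 1:1 sampling, a perfectly calibrated model would have a mean predicted risk of 13.4% in the sample, O/E = 0.50 / 0.134 = 3.7, and an intercept of ln(0.90 / 0.10) = 2.20. Over the same ranges of rate and AUC these are 2.6-4.6 and 1.7-2.3.

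**The case against.** The strongest reply is that calibration is not neglected. A Hosmer-Lemeshow statistic and decile-level observed rates are quantities, the Brier score is planned too, and the plot separates a rate shift from a slope error in most cohorts even at N = 5,000. That figure is also the low end, since Sample size says at least 500 cases and the cohort covers all of 2018 plus over three months of 2019. These points stand. A reader might infer that the planned analysis leaves no way to tell which kind of error is present; the decile plot contradicts that.

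A reader might also infer that conclusions will rest on the p-value. The plan does not say so. Nor does it predict miscalibration: it lists urgent readmission alone as a secondary LACE+ outcome, describes SQLape as predicting unforeseen 30-day readmission, and sees no relevant differences for SQLape in setting, eligibility or predictors.

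It is fair, too, that no interval is stated for the AUC, Brier score, Net Reclassification Improvement or Net Benefit. Those at least have a planned estimate. Finally, separate intervals for each model would not compare the models, so a paired comparison is needed as well.

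What the reply leaves untouched is the absence of any dedicated calibration estimate with an interval. Brier and Net Benefit respond to miscalibration but do not isolate it.

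**Conclusion.** The point holds as a gap in what is estimated. The plan will usually show the direction and rough pattern of miscalibration but not its size with an interval, although its own definition of external validation asks for calibration to be quantified. The Hosmer-Lemeshow p-value cannot fill the gap, because for a fixed error its rejection rate moves from about 32-37% to 95% between 5,000 and 20,000 patients, and it can be identical for a rate shift and a slope error.

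The consequence is modest: in the illustration, roughly one percentage point of all patients is wrongly in or out of the top risk group. These figures rest on the assumed 10% rate, AUC 0.743, logit-normal risks and the two chosen errors. The omission depends on none of them. This is a free improvement; the study can run without it.

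**What to change.** In the Statistical analysis section and the Abstract, keep the decile plot and add:

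> For each model, calibration will be reported as the observed/expected ratio, the calibration intercept (logit of predicted risk as offset) and the calibration slope, each with a 95% CI, with a smoothed calibration curve overlaid on the decile points, estimated in the full eligible cohort. Calibration conclusions will not be based on the Hosmer-Lemeshow p-value. Differences in calibration between models will be given with paired bootstrap intervals on the same patients.

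Three conditions go with it:
- Apply this mainly to the primary 30-day outcome. The secondary outcome is narrower: same diagnostic category, and "occurred within 18 days after the index/preceding hospital discharge date". Report the same measures there, but state that 30-day all-cause predictions are expected to give O/E below 1 by definition of that outcome.
- If cases and controls are sampled 1:1, reweight to the true readmission rate first.
- Confirm that the SQLape plugin returns a probability before taking logits, since the protocol describes a Poisson model.

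The cost is two short logistic fits for each of six model-outcome pairs, a bootstrap loop in R, one check of the SQLape output scale and a change of wording. No new data are needed.
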